1 TITLE PAGE

Study title: A prospective, single arm, open label post market study assessing the safety and efficacy of Nerivio for the treatment of migraine in children under the age of 12

Test Device: Nerivio

Indication studied: Acute treatment of migraine

Study description: Prospective, single arm, open label post market study

Sponsors: Theranica Bioelectronics Ltd

Protocol: RWE-009

Clinical Phase: Post market study

Study period: First user first treatment - May 2020
Last user last treatment - October 2023

Investigators: [name] [name]

Statistician: [name].
Koren Statistics
[name]

2 RWE-009 Study Protocol

Title	A prospective, single arm, open label post market study assessing the safety and efficacy of Nerivio for the treatment of migraine in children under the age of 12
Investigational Device	Nerivio is an FDA-approved remote electrical neuromodulation (REN) device for the acute and/or preventive treatment of migraine with or without aura in patients 12 years of age or older. Nerivio delivers transcutaneous electrical stimulation to the upper arm to induce conditioned pain modulation (CPM) that activates a descending endogenous analgesic mechanism. The treatment is self-administered and controlled by a smartphone application.
Objectives	The study assessed the safety and efficacy of Nerivio for acute treatment of migraine in children under the age of 12.
Participant Population	Children who were prescribed with the Nerivio device for the treatment of migraine and were under the age of 12.
Sample size	The sample size was defined as all Nerivio users in the Nerivio database under the age of 12 in the day of their first treatment
Inclusion Criteria	
• Prescribed with Nerivio device for the treatment of migraine• Age under 12 at their first Nerivio treatment• Treat with Nerivio at least once
Exclusion Criteria	
• Treatments shorter than 30 minutes
Study Design	A prospective, data analysis of users that met the inclusion criteria was performed. All data that were reported prior and following the treatments by the users using the electronic diary within the Nerivio application were downloaded from Theranica server in an unidentified manner.
Primary endpoint - Safety	Rate of Device Related Adverse Events Incidence of device-related adverse events (DRAEs) reported by subjects. a) Percentage of patients reporting DRAEs b) Severity of reported DRAEs

Secondary endpoints - efficacy	
Consistent Headache Relief at 2 Hours Post-treatment.
 
The proportion of subjects reporting headache relief at 2 hours post-treatment in at least 50% of all their treatments.
 
Consistent Freedom from Headache at 2 Hours Post-treatment.
 
The proportion of subjects reporting freedom from headache at 2 hours post-treatment in at least 50% of all their treatments.
 
Freedom from a specific migraine associated symptom.
 
Freedom from a specific migraine associated symptom was calculated as the percent of patients reporting the presence of that symptom at baseline, and the lack of that symptom at 2-hours post-treatment in at least 50% of all their treatments.
 
Per the ICHD-3, migraine associated symptoms are:
 
a) Hyper sensitivity to light (phonophobia)b) Hyper sensitivity to sound (phonophobia)c) Nausea (with or without vomiting) 
Functional disability relief
 
Functional disability relief was calculated as decrease of at least one level of functional disability from baseline to 2-hours post-treatment in at least 50% of all their treatments.
 
Disability levels are (0) none (full function), (1) mild disability, (2) moderate disability, and (3) severe disability.
 
Freedom from functional disability
 
Freedom from functional disability was calculated as decrease from any disability level (3, 2, or 1) at baseline to no disability (i.e., return to full function) at 2-hours post-treatment in at least 50% of all their treatments.

Exploratory efficacy endpoints	
Use of migraine medications
 
Treatment patterns of Nerivio use as a standalone treatment vs. in combination with medications were extracted from the 2-hours post-treatment reports, as the percentage of treatments in which no rescue headache medications were used (Nerivio standalone), or Nerivio was used with over-the-counter (OTC) medications, or with prescription medications (Rx).
 
Nerivio treatment stimulation intensity
 
Treatment intensity (stimulation current) is set by patients via the smartphone app and automatically recorded. The average intensity over all treatments per patient was calculated to provide personal intensity levels, which was used for the analyses. Average personal intensity levels and the range for 80% of the users were calculated over the patient cohort.
 
Nerivio utilization
 
Average (and/or median) of number of Nerivio treatments per month. A specific cohort of this outcome considers safety in patients who use the device at high frequency, close to the every-other-day regime of preventive treatment.

Datasets	
1. Intent to treat analysis set (ITT) The ITT analysis set includes all users who had at least one treatment2. Modified intent to treat analysis set (mITT) The mITT analysis set includes all ITT participants who had at least 2 treatments with prospective electronic diary reports at the beginning of the treatment ("baseline") and 2 hours post the beginning of the treatment.
Data Analysis	The ITT analysis set was used for the safety assessments and the mITT analysis set was used for the efficacy assessments.

STATISTICAL CONSIDERATIONS FOR RWE-009 STUDY

The study hypothesis was that treatments of migraine with the Nerivio device in children will be as safe and effective as previously described in adolescents and adults.

DATA COLLECTION

BASELINE DATA

Baseline participant characteristics (age, gender) were collected from the Nerivio account of each participant.

TREATMENT DATA

Treatment data was retrieved from the Nerivio app for each treatment. Data includes automatic parameters (e.g time of treatment, location, device serial number, treatment intensity etc...) and individual information completed by the participant (pain level before and after the treatments, migraine symptoms, functional disability before and after the treatment etc...)

COMPUTER SOFTWARE

All statistical analyses and data presentations, including tabulations and listings, were performed using the SAS version 9.4 software.

STATISTICAL ANALYSIS

Demographic and Baseline Analysis

Demographic and baseline condition related characteristics will be tabulated and compared between the participant age data type. Continuous variables will be summarized by a mean, standard deviation, minimum, median and maximum and categorical variables by a count and percentage.

Safety Endpoints Analysis

The rate of device related adverse event (DRAE) was calculated ad the number of reported DRAE divided by the number of participants in the study.

Efficacy Endpoints Analysis

All the endpoints will be calculated for Qualified Attacks only, Qualifies treatement was defined as

- 1 - Attacks treated with Nerivio for at least 30 minutes
- 2 – Pre and post treatment data was reported by the participant for the specific treatment
- 3 – No rescue medications were taken before and during the 2 hours post treatment, according to the participant report

Consistent efficacy was conducted in cases where at least two qualified treatments were performed. Patients who experienced the outcome (e.g., pain freedom) in at least 50% of their reported treatments, during which they did not report the use of rescue medications, were considered responders.

Headache pain and functional disability were rated at baseline and at 2 h post-treatment on a 4-point scale: severe, moderate, mild, or none. Migraine associated symptoms (photophobia, phonophobia, and nausea/vomiting) were marked as present or not.

Pain relief was calculated as a decrease from severe or moderate levels at baseline to mild or none at 2 h posttreatment.

Functional disability relief was calculated as any improvement in disability from baseline to 2 h posttreatment.

Pain/functional disability freedom was calculated as a decrease from any pain/disability level at baseline to none at 2 h post-treatment.

Freedom from a specific migraine-associated symptom was calculated as the percentage of patients reporting the presence of that symptom at baseline and the lack of that symptom at 2 h post-treatment. Freedom from at least one associated symptom was calculated as the percentage of patients in which one or more associated symptom(s) were reported at baseline and the lack of at least one of those symptoms at 2 h post-treatment.

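### Every defined safety measure counts only device-related events, the attribution step is unspecified, and no adverse event measure independent of attribution stands beside it

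*Combined protocol and SAP*

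**What the plan says.** The *Primary endpoint - Safety* row of the protocol table defines the endpoint as the "Incidence of device-related adverse events (DRAEs) reported by subjects", with two components: "a) Percentage of patients reporting DRAEs b) Severity of reported DRAEs". Both are confined to DRAEs.

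*Safety Endpoints Analysis* gives the one formula for safety, "the number of reported DRAE divided by the number of participants in the study". *Data Analysis* adds the population: "The ITT analysis set was used for the safety assessments". The ITT set is all users with at least one treatment.

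The title page gives the design: "Study description: Prospective, single arm, open label post market study". *Investigational Device* describes approval for patients aged 12 or older, while the study population is under 12. The hypothesis in the statistical section is that treatment in children "will be as safe and effective as previously described in adolescents and adults". No reference rate or margin is attached to it.

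On data sources, *Study Design* says that users' reports "using the electronic diary within the Nerivio application were downloaded from Theranica server in an unidentified manner". *Treatment Data* lists what participants enter: "pain level before and after the treatments, migraine symptoms, functional disability before and after the treatment etc". That open-ended list names neither adverse events nor relatedness.

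The text supplied does not say who judges relatedness, what criteria or categories are used, or what happens when relatedness is missing or unclear. It defines no all-cause and no serious adverse event measure. The *Nerivio utilization* entry mentions safety in high-frequency users but defines no measure for it.

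**The concern.** A rate of device-related events depends on two things: which events occurred and which were put down to the device. Here the second is left open. There is no control arm to show how often such events occur in these children without the device, and use of the device is known to everyone. The attribution therefore cannot be checked from within the study.

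A captured event that was not classed as related would appear in no defined safety result, even if the plan were followed to the letter. This matters most in an age group outside the approved range, because a count limited to device-related events presumes some knowledge of what the device causes at that age. A claim of safety comparable with older patients would rest on this one figure.

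The two definitions also differ in unit. The protocol table gives a percentage of patients, while the formula divides a number of events by participants.

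**Working it through.** **No figure to reproduce.** The documents state no sample size, expected DRAE rate, margin or alpha. All numbers below are assumptions chosen to show direction and mechanism.

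**Step 1: which way can attribution move the rate?** Let T be the rate of truly device-caused events, U the rate of other events, s the share of T classed as related, and f the share of U classed as related. Then

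- reported DRAE rate = s·T + f·U
- all-cause rate = T + U

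Since s and f are at most 1, the reported rate cannot exceed the all-cause rate. Against T, it is too high when f·U > (1 − s)·T and too low when the inequality is reversed.

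With an assumed all-cause rate of 10%:

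| T | U | s | f | Reported DRAE rate | Against T (points) | Against all-cause (points) |
|---|---|---|---|---|---|---|
| 5% | 5% | 0.5 | 0 | 0.5×5 + 0×5 = 2.5% | −2.5 | −7.5 |
| 8% | 2% | 0.8 | 0.2 | 0.8×8 + 0.2×2 = 6.8% | −1.2 | −3.2 |
| 5% | 5% | 0.8 | 0.2 | 0.8×5 + 0.2×5 = 5.0% | 0.0 | −5.0 |
| 2% | 8% | 0.8 | 0.2 | 0.8×2 + 0.2×8 = 3.2% | +1.2 | −6.8 |
| 2% | 8% | 1 | 0.5 | 1×2 + 0.5×8 = 6.0% | +4.0 | −4.0 |

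The three middle rows use the same quality of attribution (s = 0.8, f = 0.2), yet the error runs from −1.2 to +1.2 points. Its sign depends on the unknown mix of events.

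**Step 2: what does the missing default do?** Assume 100 children, ten of whom have one event each: 2 clearly related, 3 clearly unrelated, 5 unclear.

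- Unclear counted as not related: 2/100 = 2%.
- Unclear counted as related: (2 + 5)/100 = 7%.
- All-cause rate: 10/100 = 10% under either default.

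Only the last figure does not depend on attribution.

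**Step 3: patients or events?** In Step 2 each child has one event, so the two units agree. If the 2 clearly related events came from one child, the formula in *Safety Endpoints Analysis* would still give 2/100 = 2%, but the percentage of patients in the protocol table would be 1/100 = 1%. The two definitions agree only when no child reports more than one DRAE.

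**The case against.** A device-related endpoint is not in itself an error; it targets what the device does, and an all-cause rate measures something else. That stands. The gap is the lack of a stated attribution rule and of an all-cause count beside the endpoint. The absent rule alone would be no more than missing detail.

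A reader might infer that attribution can only lower the rate, so that every error favours the device. The documents do not support this. It is true against the all-cause rate, where it follows from DRAEs being a subset. Against the device-caused rate, families who know the device was used may blame it for background complaints. Nausea, for instance, is a listed migraine symptom.

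A reader might also infer that an unblinded assessor removes events after they are reported. The endpoint speaks of events reported by subjects, which may mean that the family makes the attribution. Neither reading is settled.

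Finally, the remedy depends on data whose existence is not shown. If only DRAEs were captured, no all-cause table can be made. If relatedness was never recorded, counting unknown as related turns the DRAE rate into an all-cause rate, which could be a large change. The last treatment was in October 2023 and the safety analysis is described in the past tense, so a rule may now have to be post hoc. All of this stands and shapes the fix, but it does not remove the need for one.

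**Conclusion.** The point holds in this form. The defined safety measures are limited to device-related events, the owner and criteria of the attribution are not stated, and no measure free of attribution is defined. The reported rate is bounded above by the all-cause rate and may be too high or too low for the truly device-caused rate. The documents do not support a claim of bias in the device's favour.

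The size cannot be determined, because no counts are given. The shift from 2% to 7% in the working rests wholly on assumed counts and shows only that the default for unclear events can dominate a low rate. The gap between a DRAE rate and an all-cause rate is a difference between two quantities and should not be read as the bias of one of them.

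The change should be made. An all-cause count is cheap where the events were captured, and it keeps an unanticipated event in a new age group visible whatever its classification. The inconsistency between patients and events stands regardless of any assumption.

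**What to change.** 1. Beside the DRAE rate, report the percentage of ITT children with any reported adverse event and with any serious adverse event, regardless of cause, from all captured events. If only DRAEs were captured, say so as a limitation of the safety conclusion.
2. State who attributes events to the device and by what criteria.
3. Count an event with unknown or undetermined relatedness as device-related, or show the rate under both classifications. If relatedness was largely unrecorded, showing both is the more informative choice. Label the rule post hoc if it is set after the events were reviewed.
4. Use the percentage of patients with at least one event in both *Primary endpoint - Safety* and *Safety Endpoints Analysis*. A count of events may be given in addition, labelled as such.

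The cost is some wording and one more table, provided that the events were captured. The stated rate may be higher; by how much cannot be known from the documents.

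### Read literally, the 50% responder rule for pain relief, disability relief and disability freedom counts treatments that cannot succeed, and the plan does not say whether they were removed

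*Combined protocol and SAP*

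**What the plan says.** The threshold and the outcome are defined separately.

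- **Threshold, protocol table (Secondary endpoints - efficacy).** Headache relief is "The proportion of subjects reporting headache relief at 2 hours post-treatment in at least 50% of all their treatments". Disability relief and disability freedom use the same 50% of all treatments.
- **Threshold, Efficacy Endpoints Analysis.** Responders are "Patients who experienced the outcome (e.g., pain freedom) in at least 50% of their reported treatments", limited to treatments without reported rescue medication. Also, "All the endpoints will be calculated for Qualified Attacks only". A qualified treatment lasted at least 30 minutes, has pre- and post-treatment data, and involved no rescue medication.
- **Minimum number.** "Consistent efficacy was conducted in cases where at least two qualified treatments were performed". The mITT set in the Datasets row asks for "at least 2 treatments with prospective electronic diary reports at the beginning of the treatment" and at 2 hours.
- **Outcome.** "Pain relief was calculated as a decrease from severe or moderate levels at baseline to mild or none at 2 h posttreatment". Disability relief is a drop of one level or more, so it cannot occur from level 0. For freedom, "Pain/functional disability freedom was calculated as a decrease from any pain/disability level at baseline to none at 2 h post-treatment".
- **Scale.** "Headache pain and functional disability were rated at baseline and at 2 h post-treatment on a 4-point scale: severe, moderate, mild, or none". Mild and none are therefore possible baseline ratings, and the protocol table lists disability level 0 as full function.

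**The concern.** No qualified-treatment criterion and no part of the mITT definition concerns the baseline level. They ask that a baseline value was reported, not that it reached any level. Followed literally, the relief and disability responder rates mix two things: how often treatment worked, and how often the child started in a state from which success was possible. A low rate could mean poor response or many mild starts.

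The study hypothesis sets these children against earlier results in older patients. The documents do not show which denominator those results used, so a reader cannot tell whether like is compared with like.

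Other endpoints are touched less clearly. Pain freedom is affected only by treatments started without pain. For freedom from a specific symptom, the text leaves open whether treatments without that symptom at baseline count.

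**Working it through.** The documents state no responder rate, sample size or power, so there is no figure to reproduce. The check has a deterministic part and an illustrative part.

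**1. One child, by the written definitions.** Take 5 qualified treatments: 3 start mild and end pain-free; 2 start severe and are relieved.
- Pain relief, literal: 2/5 = 40%, a non-responder.
- Pain relief, moderate or severe starts only: 2/2 = 100%, a responder.
- Pain freedom: at least 3/5 = 60%, a responder.

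**2. Model (all inputs assumed).** Let n be the number of qualified treatments, q the chance that a treatment starts in the required state, and r the chance of success if it does, with independent treatments. K ~ Bin(n, q) treatments are at risk, and S given K ~ Bin(K, r) succeed.
- Literal rate, all children: P(S ≥ n/2), where S ~ Bin(n, qr).
- At-risk rate, children with at least one at-risk treatment: P(S ≥ K/2 | K ≥ 1).

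**3. One case in full: n = 3, q = 0.9, r = 0.6.**
- Literal: qr = 0.54, and 3 × 0.54² × 0.46 + 0.54³ = 0.4024 + 0.1575 = 0.560.
- At-risk: (0.027 × 0.60 + 0.243 × 0.84 + 0.729 × 0.648) / 0.999 = 0.6927 / 0.999 = 0.693.
- The gap is 13 points. Children with K = 2 contribute 0.243 × (0.84 − 0.36) = 0.117 of it. They need 2 of 2 under the literal rule and 1 of 2 under the at-risk rule. Part of that difference is rounding, because half of 3 treatments becomes 2.

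**4. Results at r = 0.6** (gaps from unrounded rates):

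| n | q | Literal | At-risk | Gap, points |
|---|---|---|---|---|
| 6 | 0.95 | 77.7% | 78.8% | 1 |
| 6 | 0.90 | 72.8% | 76.9% | 4 |
| 6 | 0.80 | 61.8% | 75.2% | 13 |
| 6 | 0.70 | 49.7% | 74.6% | 25 |
| 3 | 0.95 | 60.4% | 67.4% | 7 |
| 3 | 0.90 | 56.0% | 69.3% | 13 |
| 3 | 0.80 | 47.0% | 71.8% | 25 |
| 3 | 0.70 | 38.1% | 72.6% | 34 |

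- With n = 2 the rates are 78.8% and 79.6% at q = 0.9, and 66.4% and 72.9% at q = 0.7. This gap arises only because children with no at-risk treatment leave; among the same children there is none.
- With n = 6 and r of 0.4, 0.6 or 0.8, the gap is 2 to 4 points at q = 0.9 and 19 to 25 points at q = 0.7.
- With q and r each varying between children (beta-distributed, intraclass correlation 0.3, n = 6, mean r = 0.6, simulated), the gap is about 3, 6, 12 and 20 points at q = 0.95, 0.9, 0.8 and 0.7.

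**5. Children who can never respond under the literal rule, P(K < n/2).** For n = 6: 0.1%, 1.7% and 7.0% at q = 0.9, 0.8 and 0.7. For n = 3: 2.8%, 10.4% and 21.6%.

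**6. Direction.** If S ≥ n/2 with n ≥ 2, then K ≥ S ≥ 1, and S ≥ K/2 because K ≤ n. Every literal responder is therefore also an at-risk responder under the one-treatment minimum.

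**The case against.** The strongest objection is that the outcome wording already restricts the treatments: a decrease from severe or moderate pain can be read as describing which treatments are evaluable, and the symptom definition likewise refers to presence at baseline. That reading is available. But those sentences define success, while the denominator is given separately, in both places, without that limit. Two competent analysts could program different rates.

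Three further objections stand in whole or in part.

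- **A denominator is stated.** The analysis section does give one: qualified, rescue-free treatments. A reader might infer that the denominator is missing altogether. It is not; only the baseline condition is open.
- **The literal rule works against the device.** It can only lower these rates relative to the at-risk rule with a one-treatment minimum. An at-risk version adopted after the last treatment in October 2023 can only raise them.
- **The at-risk rate is not a clean measure either.** A 50% cut-off on fewer treatments shifts with presence too. At 60% success, as presence falls from 100% to 70%, it moves from 84% to 73% with 2 treatments, from 82% to 75% with 6, and up from 65% to 73% with 3. It also lets 1 of 1 count as consistent response. A reader might infer that the at-risk rule is the right one and should replace the written rule; the documents do not support that.

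**Conclusion.** The point holds as a matter of definition. As written, the three endpoints count treatments that cannot succeed, and the documents do not say whether these were removed. Whether any reported rate is affected cannot be told from the documents, so it would be wrong to infer that the analysis did use the literal rule or that the device's effect was understated by a known amount.

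The illustrative gaps rest on assumed presence, success rate and number of treatments, and mostly on independence between treatments. They vanish if every treatment starts in the required state. It is tempting to add that they are small whenever nearly all do. That is true for 2 and 6 treatments but not for 3, where the gap is already 7 points at 95% presence and 13 at 90%, in part from rounding.

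The matter should be corrected but is not critical: the endpoints are secondary, and the primary safety endpoint is untouched.

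**What to change.** For each endpoint, in both the secondary endpoints table and the Efficacy Endpoints Analysis section, state whether treatments without the required baseline state leave the denominator, whether they count towards the two-treatment minimum, and what the analysis program did.

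Then report side by side:
1. the written rate over all qualified treatments;
2. an at-risk rate over qualified treatments with the required baseline state: moderate or severe pain for pain relief, at least mild pain for pain freedom, symptom present for symptom freedom, and disability of at least 1 for both disability endpoints.

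Show the at-risk rate with a minimum of one and of two at-risk treatments, since a single treatment cannot show consistency. Give the numbers of evaluable children and treatments per endpoint. Label as post hoc whichever version the program did not use.

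The cost is wording and a rerun on data already held. The report should state these downsides:
- With the one-treatment minimum, the at-risk rate can never be below the literal rate, so it favours the device.
- The at-risk rate still depends on how often the baseline state is present, though usually less strongly than the literal rate.
- Children are lost or thinly classified. Among children with 2 treatments at 70% presence, the one-treatment minimum keeps 1 − 0.3² = 91%, but 2 × 0.7 × 0.3 = 42% of all such children are judged on one treatment. The two-treatment minimum keeps only 0.7² = 49%, and at 60% success it drops literal responders amounting to 0.42 × 0.6 = 25% of all such children.

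### Stimulation intensity and utilization are logged automatically but labelled as efficacy, so the plan's only analysis-set rule puts them in mITT, while other wording points to ITT

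*Combined protocol and SAP*

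**What the plan says.** All of the following is in the combined protocol and SAP.

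- **Label.** In the synopsis table (section 2, RWE-009 Study Protocol), stimulation intensity and utilization stand in the row headed "Exploratory efficacy endpoints".
- **Set rule.** The Data Analysis row assigns ITT to safety and says that "the mITT analysis set was used for the efficacy assessments". Nothing is said separately about exploratory or device-logged outcomes.
- **Set definitions (Datasets row).** "The ITT analysis set includes all users who had at least one treatment". "The mITT analysis set includes all ITT participants who had at least 2 treatments with prospective electronic diary reports", at both the start of treatment and 2 hours later.
- **Source of the data.** "Treatment intensity (stimulation current) is set by patients via the smartphone app and automatically recorded". Under Treatment Data, the time of each treatment is also among the automatic parameters.
- **Population wording in the endpoints.** Intensity is averaged over all of a child's treatments and then summarised across the patient cohort, with neither set named. Within utilization, "A specific cohort of this outcome considers safety in patients who use the device at high frequency".
- **Treatment-level filters.** Efficacy Endpoints Analysis restricts all endpoints to qualified attacks: at least 30 minutes, pre and post data reported, no rescue medication. The synopsis also excludes treatments under 30 minutes at study level.

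**The concern.** A diary requirement makes sense for pain, symptoms and disability, which are known only from the diary. It has no purpose for intensity or number of treatments, which the app records regardless. Applying mITT here removes two groups whose data are in hand: children who treated once, and children who treated repeatedly but did not complete two diaries. For utilization there is a further problem. Requiring at least two treatments before a child may contribute to a measure of treatment frequency is selection on the outcome.

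The high-frequency safety cohort raises the stakes. As a safety look it belongs to ITT; as part of an endpoint labelled efficacy it belongs to mITT. Under the second reading, a child who treats very often without completing diaries would be left out of that check although the exposure is logged. The reported treatments per month and personal intensity could then describe diary-keepers but be read as the pattern in all children under 12.

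**Working it through.** The plan states no set sizes and no utilization or intensity figure, so there is nothing of its own to reproduce. Every numerical input below is an assumption, used only to see direction and possible size.

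**1. Which set does the text give?**

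| Outcome | By label and set rule | By its own wording |
|---|---|---|
| Intensity | Efficacy, so mITT | All treatments, patient cohort: closer to ITT |
| Utilization | Efficacy, so mITT | Not named |
| High-frequency safety cohort | Inside an efficacy endpoint, so mITT | A safety look, so ITT |

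No sentence settles the conflict. The qualified-attack filter adds to it: read as covering every endpoint, it would delete treatments with rescue medication and so make the exploratory medication-use endpoint impossible to describe. It cannot have been meant for all exploratory endpoints, but the plan does not say which are exempt.

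**2. Utilization, identity.** Let s be the share of ITT children outside mITT, and r their mean use relative to mITT children. If the mITT mean is m, the ITT mean is (1 − s)m + s·r·m, so

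mITT mean / ITT mean = 1 / [(1 − s) + s·r]

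| s | r = 0.1 | r = 0.5 | r = 1 | r = 1.25 |
|---|---|---|---|---|
| 0.2 | 1.22 | 1.11 | 1.00 | 0.95 |
| 0.4 | 1.56 | 1.25 | 1.00 | 0.91 |
| 0.6 | 2.17 | 1.43 | 1.00 | 0.87 |

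For example, s = 0.4 and r = 0.5 give 1/(0.6 + 0.2) = 1.25. The ratio exceeds 1 only if r is below 1.

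**3. Is r below 1 likely?** This was checked by simulating 200,000 children over a common 3-month window. Monthly rates were skewed (gamma, shape 0.8, mean 3), counts were Poisson, and each diary pair was completed with probability p regardless of use.

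| p | ITT children in mITT | ITT mean per month | mITT mean per month | Ratio | Left-out children with 2 or more treatments |
|---|---|---|---|---|---|
| 0.2 | 45.6% | 3.47 | 5.80 | 1.67 | 79% |
| 0.4 | 66.7% | 3.46 | 4.73 | 1.37 | 65% |
| 0.6 | 77.4% | 3.45 | 4.27 | 1.24 | 49% |
| 0.8 | 84.0% | 3.46 | 4.04 | 1.17 | 28% |

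Use is inflated even when diary completion is unrelated to use, because a child with more treatments has more chances to reach two diaries. The last column shows that many of the children left out are repeat users who only lack diaries.

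**4. Undefined months.** The plan does not say which months form the denominator. In a second simulation of 100,000 children, time in use was exponential with mean 3 months, p was 0.4, and the denominator was each child's own first-to-last span. With spans floored at 1 month, mean use is 3.63 (ITT) against 5.37 (mITT). With spans floored at 1 day it is 12.69 against 6.65. The direction reverses because single-treatment children receive very high rates.

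**5. Intensity.** Let d be the mITT mean minus the mean of children outside mITT. Then mITT mean − ITT mean = s·d. At s = 0.4, d = 10, 5, 0 and −5 intensity units give +4, +2, 0 and −2. The documents say nothing about d.

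**The case against.** The best reply is that use of mITT is only inferred from a row heading. The intensity text speaks of all treatments, users and the patient cohort, which sits better with the ITT definition. The high-frequency cohort is expressly about safety, and safety has an explicit rule: ITT. On that reading nothing is lost, and the plan needs only a clarification. The outcomes are also exploratory and descriptive.

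Much of this stands. The documents do not establish that mITT was used, nor that a frequent user without diaries was left out of the safety look. Logged exposure is also only half of a safety assessment: adverse events are those that subjects report, and the channel is not described. But the reply leaves the endpoint wording and the only set rule pointing to different sets, and an analyst who follows the rule as written gets the worse one.

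A reader might go further and infer that mITT overstates both use and tolerated intensity because it removes children who tried the device and stopped. The documents do not support this. Nothing links intensity to stopping or to diary completion; the direction for use depends on an undefined denominator; and mITT also removes continuing users who skip diaries.

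**Conclusion.** The concern holds as a conflict in the plan with a rule that, taken literally, gives an unsuitable set for two device-logged outcomes and for the high-frequency safety cohort. Over a common time window, mITT would probably overstate treatments per month. The true size cannot be computed from the documents; the ratio of 1.17 to 1.67 rests on the assumed use distribution, a 3-month window and diary completion of 20% to 80%. There is no bias if children outside mITT use the device equally often, understatement if they use it more, and possible reversal with own-span denominators. For intensity, neither size nor direction is known. The primary adverse-event result, which uses ITT, and the responder endpoints, which need diaries, do not change. This should be corrected, but it does not threaten the main conclusions.

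**What to change.** 1. In the Data Analysis row, limit mITT to diary-based efficacy outcomes. Assign ITT to stimulation intensity, utilization and the high-frequency safety cohort, using all recorded treatments whether or not a diary was completed.
2. Under Efficacy Endpoints Analysis, state that the qualified-attack filter does not apply to these outcomes. Changing the Data Analysis row alone would leave the diary requirement in force treatment by treatment.
3. State whether the synopsis exclusion of treatments shorter than 30 minutes applies to them, since it conflicts with using every recorded treatment.
4. Define the months denominator and how single-treatment children enter it, and report how many such children there are.
5. Show the mITT figures alongside as a sensitivity analysis.

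The cost is a short text change in a few places and a re-run on data already held. Mean utilization may look lower.
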